## APPROACH

**Study Design and Criteria:** In a pilot, randomized-controlled, single-blind study, a target of 24 patients will be assigned to either receive facilitation of cPMd or facilitation of iM1 (conventional approach), delivered daily in conjunction with rehabilitation for 2 days/wk for 6 wks. They will be assigned to treatment groups using a stratified randomization scheme to minimize group imbalances on 4 key patient characteristics: (1) time post-stroke (<2 yrs vs.  $\geq$ 2 yrs), (2) cortical vs. subcortical stroke, (3) presence of active wrist extension vs. no wrist extension, and (4) paretic side (dominant vs. non-dominant). Assessments will be completed at baseline and at the end of treatment after 6 wks, except assessments for Aim 1 that will also be completed at screening and at 3-month follow-up visit (Table 1). Ten age matched healthy controls, fifteen age matched mild, and up to 5 moderately impaired participants (who will undergo rTMS and CCFES based-therapy) will also be enrolled to record comparative neural indices. The goal will be to establish age-based norms for healthy, mild, moderate, and severe neurophysiologic metrics related to EDC, FDI, Biceps, and Triceps muscles.

Table 1: Schedule of Assessments		Screening & Eligibility	Baseline (0 weeks)	End-of-Treatment (6 weeks)	Follow-up (3 months)
History, Physical & Neurological Examination		X			
Eligibility testing: Inability to elicit MEPs (TMS), i.e., MEP-		X			
Aim 1	Impairment (UEFM)			X	X
	Functional Ability (WMFT)		X	X	X
	Distal movement (Grasp/Grip Strength)		X	X	X
	Patient-perceived Disability (SIS-16)		X	X	X
Aim 2	IHI imposed on iM1 (TMS)		X	X	
	Inter-hemispheric connectivity (resting state fMRI)		X	X	
Aim 3	Uncrossed pathways or Ipsilateral MEPs (TMS)		X	X	
	Ipsilesional corticospinal damage (DTI)		X		
Aim 4					

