**STATISTICAL ANALYSIS:** For analysis of aims 1, 2 and 3, linear mixed effects models will be used to compare change in UEFM (primary endpoint), WMFT rate, functional ability, grip strength, SIS, IHI, functional connectivity, and ipsilateral MEP area from baseline to end-of-treatment (and 3-month follow-up) between groups. Models will account for spasticity, baseline wrist extension (none;  $\leq 10^\circ$ ;  $> 10^\circ$ ), lesion size/location, time post-stroke, side of paresis, biologic variables (e.g., sex) and handedness. Bivariate (Pearson's) correlation will be used to explore relationships between change in function and change in IHI, functional connectivity and ipsilateral MEP area. Chi-square or Fisher's Exact test will help compare the frequency of responders (those achieving  $\geq 5.2$ -point UEFM gain [84]) and patients showing restoration of ipsilesional MEPs (MEP+) between groups. For aim 4, regression models will capture the influence of baseline  $FA_{\text{Asymmetry}}$  upon improvements associated with facilitation of cPMd vs. iM1, and separately the influence of baseline UEFM and wrist extension.

Additional data analysis will be conducted using quantum machine learning (QML) to develop a classification model for assessing the functional capacity of stroke patients to use the affected upper extremity. We will utilize behavioral outcome measures signifying the functional capacity collected during this study. The ultimate goal of this analysis is to discern variations in functional capacity among individuals affected by stroke for tailoring rehabilitation interventions to each patient's specific needs.

**Potential Pitfalls and Alternative Solutions:** *If not all patients can elicit ipsilateral MEPs in the paretic muscle*, we will compare groups upon the frequency of evidence of these MEPs after treatment (Chi-square/Fisher's Exact) [4, 52, 57, 58, 60-73]. *If effects of cPMD facilitation are weak*, we will perform sub-group analyses based on baseline wrist extension to determine which category of patients shows the best response. We will also determine what level of baseline FAAsymmetry, connectivity, impairment (UEFM) predicts response vs. non-response (based on attainment of 5.2-point UEFM gain [84]). *Anticipating that cPMD facilitation may have effects on bilateral control*, we will adopt bimanual test used in our recent study [159].

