### Sample size Estimation and Power

**Analysis:** Table 2 shows sample size estimations based on two-sample t conducted across difference scores between groups. We expect to enroll 22 subjects but in accounting for ~10% attrition, a total of 24 subjects will be enrolled.

Table 2: Sample Size Estimation

Aim	Metric	cPMD vs. iM1		Alpha	80% 85% 90% 95%			
		UEFM	IHI		14	16	18	22
Aim 1		9±1.41 vs. 4.3±3.56	-9.25±5.89 vs. 6±14.05	0.05	14	16	18	22
Aim 2				0.05	20	22	26	30
Aim 3	Ipsilateral MEP	311.63±29.96 vs. 255.75±93.29		0.05	22	24	38	46
Aim 4	DTI $\alpha$ UEFM	15% diff. in slopes		0.05	18	20	23	28

**IMPACT:** While greater damage produces greater impairment following stroke, it also generates a widespread plastic response involving the intact cortices in the contralesional hemisphere. Although this response may not be sufficient to support complete recovery, it is likely to support more recovery than what is otherwise possible to achieve [4]. Demonstrating that facilitating these intact areas can lead to restoration of paretic-limb function in patients who fail to benefit from any therapies on account of extensive damage will carry tremendous clinical impact, provide the impetus to develop targeted therapies and depart from conventional beliefs that have always disparaged the potential offered by the intact hemisphere.

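### If the cPMd effect is weak, the protocol searches wrist-extension categories for the best responders; with no true effect, the chosen category would show a spurious advantage of about 1 to 1.5 UEFM points

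*Protocol*

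**What the plan says.** The search is in the Protocol under Potential Pitfalls and Alternative Solutions. Its trigger is "If effects of cPMD facilitation are weak"; its content is "we will perform sub-group analyses based on baseline wrist extension to determine which category of patients shows the best response". No threshold defines a weak effect. Best response could mean the change within the cPMd arm or the cPMd-minus-iM1 difference (iM1 is the ipsilesional primary motor cortex). No test, alpha, interaction term, adjustment or exploratory label is given.

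Three other places bear on it:

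- **Statistical Analysis, Aim 4.** Regression models are planned, with no trigger, for baseline FA asymmetry as a modifier of improvement with cPMd versus iM1, and "separately the influence of baseline UEFM and wrist extension".
- **Number of categories.** The mixed models carry wrist extension at three levels: none, up to 10 degrees, more than 10 degrees. Study Design and Criteria stratifies randomisation on two: "presence of active wrist extension vs. no wrist extension". The search does not say which it uses.
- **SAP.** It lists within-group and between-group comparisons of change, with Holm-Bonferroni correction for the motor outcomes. It lists no subgroup analysis.

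**The concern.** The analysis starts only after a disappointing result, and its stated aim is to find a maximum. The largest of several noisy estimates is biased upward whether or not a p-value is attached. With about 22 evaluable patients, each category holds only a handful per arm, so the noise is large.

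What is at stake is mainly the next study. Under Preliminary Approach, this team took responder criteria from a 15-patient experiment and used them to set enrolment here, and Aim 4 names responder stratification as a purpose. A best category chosen from this trial could be used in the same way, with an inflated effect attached. A weak overall result could also be presented as success in one category.

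**Working it through.** **1. The plan's own figure.** Sample size Estimation and Power Analysis says "Table 2 shows sample size estimations based on two-sample t conducted across difference scores between groups" and gives UEFM change as "9±1.41 vs. 4.3±3.56".

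- Difference: 9 − 4.3 = 4.7.
- Root-mean-square SD: √[(1.41² + 3.56²)/2] = √[(1.99 + 12.67)/2] = 2.71.
- Standardised difference: 4.7/2.71 = 1.73.

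A two-sided 0.05 unequal-variance t-test with 1:1 allocation (assumed; no ratio is stated) gives total N of 14, 16, 18 and 22 for 80, 85, 90 and 95% power. This matches Table 2, so 2.71 and 11 per arm are used below. The documents give no error rate or bias for the search itself.

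**2. Selection bias by formula, no true effect.** Category differences are independent with standard error SE = 2.71 × √(2/m), where m is patients per arm per category. The expected maximum is 0.564 × SE for two and 0.846 × SE for three.

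- Two: m = 11/2 = 5.5; SE = 2.71 × 0.603 = 1.63; bias = 0.564 × 1.63 = 0.92 points.
- Three: m = 11/3 = 3.67; SE = 2.71 × 0.738 = 2.00; bias = 0.846 × 2.00 = 1.69 points.

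**3. Selection bias by simulation.** The true category split is not given. Patients were therefore placed in categories at random, a category was eligible only with at least two patients per arm, and the search ran only after a main test with p ≥ 0.05.

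| Category probabilities | Mean best-category cPMd − iM1 difference | Main test or any category p < 0.05 |
|---|---|---|
| 1/2, 1/2 | about 1.0 | about 12% |
| 1/3, 1/3, 1/3 | about 1.5 | about 15% |
| 0.50, 0.35, 0.15 | about 1.1 | about 13% |

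The last column uses a common SD of 2.71. The middle column is practically the same with 1.41 and 3.56 in the two arms. If every category is forced to be populated, the bias is 0.9 to 1.0 points (two) and 1.6 to 1.8 (three), in line with step 2. The random-split figures for three categories are lower because a sparse category often drops out.

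**4. False findings, under an added assumption.** Suppose each category is tested at an unadjusted two-sided 0.05 and any hit is reported.

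- Categories alone, all testable: 1 − 0.95² = 9.75% (two); 1 − 0.95³ = 14.3% (three).
- Main test or any category: the last column above; 11.9% and 16.7% if all categories are populated.
- Any category, given a non-significant main test, all populated: 7.2% and 12.4%.
- Favouring cPMd only, main test or any category: about 6% (two) and 6.5 to 8% (three), against a nominal 2.5%.

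**5. When there is a true effect.** With a uniform effect of 2.0 points and populated categories, the best category averages 2.9 (two) or 3.7 (three). Restricted to trials whose main test was non-significant, it averages 2.3 or 3.1, while the overall estimate averages 1.3.

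**6. Power of the interaction.** With two categories of 6 and 5 per arm, the SE of the difference between category effects is 2.71 × √(2/6 + 2/5) = 2.32. An interaction as large as the whole planned effect gives 4.7/2.32 = 2.03, against a critical value of 2.10 on 22 − 4 = 18 degrees of freedom. Power is therefore slightly below one half.

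**The case against.** The trial is a pilot, and wrist extension is not a variable picked after the fact: it is a randomisation stratum, a model covariate and a named modifier under Aim 4, whose title marks it as exploration. The protocol promises no test within categories and no efficacy claim from one. Chance alone would seldom give a best-category difference as large as the 5.2-point benchmark: about 0.1 to 3% of null trials in the populated-category runs.

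Much of this stands. A reader might infer that the plan multiplies the false-claim rate two- to threefold. The documents do not support that as a statement about the plan: it needs unadjusted 0.05 tests in every category and a rule that any hit becomes a claim, and neither is written. Without such a claim the error rate of the primary comparison is unchanged. The two-sided rates also include the main test's own 5% and hits favouring iM1. Spurious advantages of up to 2 points in the random-split runs likewise require the iM1 SD of 3.56 in both arms, although Table 2 gives 1.41 for cPMd.

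The objection does not remove the selection bias, which needs only the rule as written. Naming wrist extension in advance supports the Aim 4 regression, not a search started by a weak result.

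**Conclusion.** The concern holds as a point about selection bias. Following the written rule with no true effect gives the chosen category a spurious cPMd advantage of about 1.0 UEFM point with two categories and 1.1 to 1.5 with three. That is roughly 20 to 30% of the 5.2-point responder benchmark (1.0/5.2 = 19%; 1.5/5.2 = 29%). It rests on 11 per arm, normally distributed changes, Table 2's SDs, best response read as the between-arm difference, and assumed category splits.

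The rise in false findings from 5% to about 12% or 13 to 15% is conditional on testing and reporting rules that the protocol does not state, and should be quoted only with that condition. A reader might also take the SAP's silence to mean that the search was dropped, or its Holm-Bonferroni wording to cover it; the SAP says neither.

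**What to change.** In Potential Pitfalls and Alternative Solutions, replace the triggered search with the arm-by-wrist-extension interaction implied by the Aim 4 regression, run whatever the main result. Specifically:

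- Use the two levels of the randomisation stratum, or say why the three levels of the model covariate are used.
- Report the cPMd-minus-iM1 difference in every category with a confidence interval.
- State that the result is hypothesis-generating and cannot replace a non-significant primary comparison.

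The last statement is needed even if the category tests are adjusted. Holm within the categories holds the subgroup family at about 5%, but the whole procedure stays at 8.2 to 8.9% if a subgroup hit may rescue the primary result.

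The SAP has no subgroup sentence to delete. As it is written in the past tense, it should say whether any wrist-extension analysis was run and, if so, describe it in these terms.

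The cost is a few lines of text and no new data. The interaction test has low power in about 22 patients, so a null result would say little, and a fallback analysis is lost.

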In this Transformational Project Award (TPA), we take our exploratory AHA findings to the 2nd stage and test whether facilitating the intact, contralesional motor cortices would yield the maximum improvement in paretic-limb function in moderately/severely impaired patients, based on plastic mechanisms most pertinent to patients' recovery (*scientific premise*) (Fig. 1). Our in-progress AHA study and other studies have revealed that intact, contralesional motor cortices make functionally significant contributions to paretic-limb movement when there is extensive ipsilesional damage. Contralesional motor cortices reduce IHI and excite uncrossed output to support movements of the proximal and distal paretic-limb, including reaching and grasp/grip. Therefore, in our recent AHA study, facilitation of the contralesional motor cortices, particularly the contralesional dorsal premotor cortex (cPMd), given just for a single session, leads to 20% more improvement in paretic-limb reaching speed than the conventional approach facilitating iM1 in moderately/severely affected patients [3]. Here, we will test whether the promise and mechanisms of facilitating cPMd elicited within a single session in our recent AHA study can be consolidated to generate clinically meaningful improvements in function in moderately/severely-affected patients by applying multiple sessions in rehabilitation.

In a pilot, randomized controlled study, 24 patients will receive facilitation of cPMd or iM1 (conventional approach) in conjunction with rehabilitation given for 2 days a week for 6 weeks. Moderately/severely-impaired patients with complete loss of ipsilesional corticospinal pathways will be selected, because these patients have been shown to have the best therapeutic response to cPMd facilitation in our in-progress AHA study [3, 6]. Primary outcome will be upper limb impairment, and secondary outcomes will be tests of functional abilities, proximal reaching performance and patient-reported disability. Associated neural mechanisms will also be studied using neurophysiological and functional connectivity MRI techniques. Damage to ipsilesional corticospinal pathways will be indexed with diffusion tensor imaging (DTI).

[figure not shown]

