**AIM 4: Explore how ipsilesional corticospinal damage influences response to cPMd facilitation.** At baseline, damage to ipsilesional corticospinal pathways will be indexed using DTI. DTI enables the investigation of structural integrity and orientation of pathways *in vivo* through the estimation of magnitude and directionality of water diffusion [69, 145-149]. DTI metrics can help quantitate damage even when patients show no response to TMS due to extensive damage (MEP-) (Fig. 4B) [3, 47, 69]. High angular resolution diffusion weighted images will be acquired and analyzed using steps outlined in our work with [name] [34, 47, 91, 150-154]. Ipsilesional and contralesional corticospinal tracts will be reconstructed using probabilistic tractography [47, 91, 153, 155]. FA, a unit-less measure of white matter integrity, will be calculated [156, 157].  $FA_{\text{Asymmetry}}$  given by  $FA_{\text{Contralesional}} - FA_{\text{Ipsilesional}}/FA_{\text{Contralesional}} + FA_{\text{Ipsilesional}}$ , will be used to express integrity of ipsilesional vs. contralesional tracts. Higher values of  $FA_{\text{Asymmetry}}$  indicate severe damage. Stroke neurologist, [name], will identify lesion location (posterior limb of internal capsule (PLIC) or non-PLIC) and volume ( $\text{cm}^3$ ) [158].

**Expected outcomes and interpretations:** Based on our AHA study, we expect that improvements associated with facilitation of cPMd will vary as a function of baseline corticospinal damage [3]. This would allow identification of a threshold level of damage, beyond which patients fail to show criterion-level improvement (5.2-point gain [84]) on UEFM, necessary for responder stratification for this new approach involving facilitation of intact areas.

**Figure 4.** (A) Group rsfMRI data from moderately/severely-impaired patients (n=9) reveals areas in ipsilesional M1 and sensory cortices (S1) (MNI: X: 49 Y: 29 Z: 48) that show an increase in functional connectivity with cPMd (MNI: 26, -6, 53) (peak t-value= 3.25) following rehabilitation. (B) Examples from our work demonstrating the feasibility of successfully generating FA maps (top) and reconstructing corticospinal tracts (bottom) in patients with severe (left panel) and mild damage (right panel).

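### The fallback responder rule uses a patient's own 5.2-point UEFM gain with no arm contrast, so a marker it finds is prognostic and does not show who gains more from cPMd than from iM1

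*Protocol*

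**What the plan says.** The fallback is in the protocol's Potential Pitfalls and Alternative Solutions, under Statistical Analysis. Its trigger is that "effects of cPMD facilitation are weak". One of its steps is to find what value of baseline FA asymmetry, "connectivity, impairment (UEFM) predicts response vs. non-response (based on attainment of 5.2-point UEFM gain [84". The sentence names no test and no analysis set, and it states no comparison between arms.

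Four other places bear on it:

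- **Aim 4, expected outcomes.** The anticipated damage threshold is one "beyond which patients fail to show criterion-level improvement (5.2-point gain [84]) on UEFM". This is again the patient's own gain, and the threshold is called "necessary for responder stratification for this new approach involving facilitation of intact areas".
- **Statistical Analysis, Aim 4 regression.** It models the influence of baseline FA asymmetry "upon improvements associated with facilitation of cPMd vs. iM1, and separately the influence of baseline UEFM and wrist extension". Connectivity is not in it.
- **Statistical Analysis, responder comparison.** "Chi-square or Fisher's Exact test will help compare the frequency of responders" between groups. No baseline marker enters.
- **SAP.** It describes within-group tests over time, between-group tests of change scores, and an exploration of change in motor function against change in TMS measures. It contains no responder or baseline-predictor analysis, so it does not supply the missing contrast.

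**The concern.** Both arms are treated: "24 patients will receive facilitation of cPMd or iM1 (conventional approach) in conjunction with rehabilitation". Gains are therefore expected on iM1 too, and the planning figures in Table 2 say so. In such a trial a patient can pass 5.2 points through training, through stimulation at either site, or through measurement variation. A baseline marker that separates those who pass from those who do not describes prognosis under treatment in general.

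Hypothesis 4 asks something else: whether the advantage of cPMd over iM1 changes with the degree of damage. That is a marker-by-arm question. The trigger makes the gap matter most, because the rule is used when the cPMd advantage is small, and that is when reaching 5.2 points says least about cPMd. A general prognostic marker could then be reported as identifying patients for contralesional stimulation, although iM1 patients with the same marker value would do as well. The programme does act on such findings: criteria for best response in its short-term study became enrolment criteria here.

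**Working it through.** **Inputs from the documents.** Table 2, Aim 1 row: UEFM gain "9±1.41 vs. 4.3±3.56" (cPMd vs. iM1), alpha 0.05. Sample size: 22 evaluable patients, 24 enrolled. Responder criterion: a gain of at least 5.2 points.

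**Assumptions.** 1:1 allocation (11 per arm); normal gains; a correlation r between marker and gain that is the same in both arms. The documents give no value for r, so a range is shown.

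**Step 1. Reproduce the plan's figure.** The difference is 9 − 4.3 = 4.7. The pooled SD is √[(1.41² + 3.56²)/2] = 2.71, so the standardized difference is 1.74. A two-sided two-sample t-test with Welch degrees of freedom needs a total of 14, 16, 18 and 22 patients for 80, 85, 90 and 95% power. This matches Table 2, so the iM1 figures are usable as planning values.

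**Step 2. Responders when cPMd is no better than iM1.** Give both arms 4.3±3.56:

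P(gain ≥ 5.2) = 1 − Φ[(5.2 − 4.3)/3.56] = 1 − Φ(0.253) = 0.40.

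That is 0.40 × 11 = 4.4 responders in the cPMd arm, none of them owing anything specific to cPMd. If gains come in whole points, so that 6 is needed, the figure is 37% with a continuity correction (5.5) or 32% without.

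**Step 3. How often a purely prognostic marker is flagged.** Identical arms were simulated. The own-gain rule was represented in its mildest form: a t-test at p<0.05 of one marker between responders and non-responders, with no cut-off search. The comparator was the test of b₃ in

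gain = b₀ + b₁·arm + b₂·marker + b₃·arm×marker, on 22 − 4 = 18 degrees of freedom.

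| r (assumed) | Own-gain rule, 22 pooled | Own-gain rule, 11 cPMd | Interaction, one marker |
|---|---|---|---|
| 0 | 5% | 5% | 5% |
| 0.3 | 18–19% | 11–12% | 5% |
| 0.5 | 46–47% | 22–23% | 5% |
| 0.7 | 83% | 45–46% | 5% |

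Ranges show the spread between separate simulation runs. No marker in this model has anything to do with the difference between cPMd and iM1, so every flag read as response to cPMd is wrong.

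**Step 4. Three markers.** The interaction approach has its own multiplicity. With three independent unadjusted tests, 1 − 0.95³ = 14% of null trials flag at least one, and simulation agrees (14–15%). Holm adjustment brings this back to about 5%.

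**Step 5. Cut-off searching is a separate matter.** With no marker related to gain, taking the best cut-off by Fisher p<0.05 over three markers flags at least one in about 40% of trials (22 patients) or 15% (11 patients). That error comes from searching. It would arise with or without an arm contrast.

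**The case against.** The strongest reply is that the plan already contains the contrast. The Aim 4 regression concerns improvement with cPMd against iM1, and Table 2 sizes Aim 4 on a difference in slopes, which fits that reading. The sentence continues to baseline UEFM and wrist extension, most naturally as influences on the same contrast. Two of the three fallback markers are thus covered, and the fallback adds to that regression without replacing it. This stands. A reader might infer that the protocol never compares the arms when it looks for predictors, and the documents do not support that. What remains is that connectivity has no such contrast, and nothing requires a fallback level to be backed by the regression.

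Second, the fallback is silent rather than explicit. A reader might infer that it pools the arms, or that it must always return a level. The text says neither; such an analysis could find no predictive value.

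Third, much larger error rates can be produced. A searched cut-off over three markers, one of them prognostic at r = 0.5, fires in 91% (chi-square) or 72% (Fisher) of pooled trials. The protocol specifies no search, and with no related marker the same search already fires in 73% or 40%. Those figures mostly measure searching and should not be charged to the missing contrast.

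Fourth, Aim 4 is exploratory in a pilot study, and a weak effect need not be zero. The stratification purpose is stated under Aim 4, not in the fallback sentence. The SAP, dated 10/23/24 and written in the past tense, reports no predictor analysis. This limits the practical reach. It does not settle what a marker found by the rule would mean.

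**Conclusion.** The point holds for the fallback and for the Aim 4 damage threshold, both of which define response by the patient's own 5.2-point gain. It does not extend to the Aim 4 regression. That much is structural and rests on no assumed figure: without an arm contrast, the analysis cannot separate a predictor of benefit from cPMd over iM1 from a predictor of improvement in general.

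The size does rest on assumptions: identical arms at the iM1 planning values, equal allocation, normal gains and p<0.05. About 40% of patients would be called responders. One prognostic marker at r = 0.5 would be flagged in roughly 46–47% of pooled analyses or 22% within the cPMd arm, against about 5% for a single interaction. Over r from 0.3 to 0.7 the own-gain rule ranges from about 18 to 83% pooled and 11 to 46% within the cPMd arm. The matter is secondary to the primary UEFM comparison, but it bears directly on who may be called a cPMd responder.

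**What to change.** In Potential Pitfalls and Alternative Solutions, replace the responder-prediction sentence with wording such as:

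> Any claim that baseline FA asymmetry, connectivity or UEFM predicts response to cPMd will rest on the Aim 4 marker-by-arm interaction for continuous UEFM change, fitted in all patients of both arms. Interactions will be reported with 95% confidence intervals and Holm adjustment across the three markers. Associations of a marker with a 5.2-point gain, and any cut-off derived from them, will be reported as prognostic and exploratory.

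Add connectivity to the Aim 4 regression, and reword the last sentence of the Aim 4 expected outcomes to match. If the analyses are already complete, the same wording can govern how any predictor result is reported.

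The change needs no new data: one interaction term per marker and a few lines of text. The real cost is precision. With about 22 patients the intervals will be wide, and the trial will usually be unable to name a level for selecting patients.
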